5.2.4 Recording of Adverse Events

At each contact with the subject during the adverse event recording period (defined in [Section 5.2.1](#)), the investigator must seek information on adverse events by specific questioning and, as appropriate, by examination. Information on all adverse events should be recorded immediately in the source document, and in the appropriate adverse event module of the case report form (CRF). All clearly related signs, symptoms, and abnormal diagnostic procedures results should be recorded in the source document, though should be grouped under one diagnosis. To the extent possible, adverse events should be recorded as a diagnosis and symptoms used to make the diagnosis recorded within the diagnosis event. Do not list symptoms if a diagnosis can be assigned.

Conditions that were already present at the time of informed consent should be recorded in the Medical History CRF. Any condition listed in a subject's medical history for which the severity increases at the time of, or post-Descartes-11 infusion, should be captured as an adverse event.

Adverse events (including lab abnormalities that constitute AEs) should be described using a diagnosis whenever possible, rather than individual underlying signs and symptoms. When a clear diagnosis cannot be identified, each sign or symptom should be reported as a separate Adverse Event. The clinical course of each event should be followed until resolution, stabilization, or until

it has been determined that the study treatment or participation is not the cause. As detailed as possible, each adverse event should be evaluated to determine:

- The severity grade (CTCAE Version 5.0 Grade 1-5)
- Its duration (start and end dates)
- Its relationship to the study treatment: Is there a reasonable possibility that the AE is related to Descartes-11- No (unrelated) or Yes. If yes- is the event definitely, probably, possibly or unlikely related to the investigational treatment (Descartes-11).
- Action taken with respect to study or investigational treatment (none, dose adjusted, temporarily interrupted, permanently discontinued, unknown, not applicable)
- Whether medication or therapy taken (i.e., no concomitant medication/non-drug therapy, concomitant medication/non-drug therapy)
- Whether it is serious, as defined in [Section 5.1](#).

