All adverse events should be treated appropriately. If a concomitant medication or non-drug therapy is given, this action should be recorded on the Adverse Event CRF. Adverse events should be entered into the eCRF system within 10 working days from the knowledge of the event took place. Once an adverse event is detected, it should be followed until its resolution or until it is judged to be permanent, and assessment should be made at each visit (or more frequently, if necessary) of any changes in severity, the suspected relationship to the study treatment, the interventions required to treat it, and the outcome.

Progression of malignancy (including fatal outcomes), documented appropriately in the medical records, should not be reported as a serious adverse event. Adverse events that occur concurrently with the progression of malignancy but that are not related to disease progression (i.e., deep vein thrombosis) will be reported as an adverse event as described above.

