5.2.5 SAE and SUSAR Reporting

To ensure patient safety, every SAE and SUSAR, regardless of suspected causality, occurring during the adverse event reporting period defined in [Section 5.2.1](#) must be reported to the Sponsor within 24 hours of learning of its occurrence. Recurrent episodes, complications, or progression of the initial SAE must be reported as follow-up information is received. An SAE occurring at a different time interval or otherwise considered completely unrelated to a previously reported one should be reported separately as a new event.

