5.2.5.1 Study Sponsor Notification by the Investigator

Any SUSAR and SAE as defined in [Section 5.1](#) must be reported to the Sponsor by **email or fax within 24 hours** of knowledge of the event. To the extent possible, adverse events should be recorded as a diagnosis. Do not list symptoms if a diagnosis can be assigned. At the time of the initial notification, a serious adverse event (SAE) report form should be filled. Following parameters will be asked in the form:

- Subject information
- A description of the event (if there is a diagnosis, it should be included)
- Date of onset

- Current status
- Whether study treatment was discontinued
- The reason why the event is classified as serious
- Investigator assessment of the association between the event and study treatment
- Concomitant medications when the event happened
- Narrative summary of the event

Follow-up information on this event should be reported when received. The follow-up information should describe 1) whether the event has resolved or continues, 2) if and how it was treated, and 3) whether the patient continued or withdrew from study participation.

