5.5 Stopping Rules and Study Termination

Premature termination of the clinical trial may occur because of a regulatory authority decision, change in opinion of the IRB or medical monitor. Additionally, recruitment may be stopped for reasons of particularly low recruitment, protocol violations, or inadequate data recording. Specifically, study will be stopped if:

- Study Sponsor or a Regulatory Body decides for any reason that subject safety may be compromised by continuing the study.
- The Sponsor decides to discontinue the development of the intervention to be used in this study.

The study will be **paused if:**

- There is death that is reasonably attributed to study drug within the first 30 days after first infusion
- Two subjects with Grade 4 adverse events to vital organs that are assessed as probably or definitely related to study drug within the 14 days after last infusion

If the study is paused for the reasons above, the PI and members of the study team will meet in person or by teleconference within 24 hours of the event to have a thorough discussion of the event. Meeting minutes capturing the review of any ongoing investigations, including next steps in the management of the subject and any proposed changes to the protocol will be forwarded to the medical monitor. If all parties agree as to the event resolution, then the pause will be lifted. If the study is paused for manufacturing reasons, the Sponsor will make recommendations for process improvements to be implemented. Pending successful completion of a process validation run, the manufacturing pause will be lifted.

6 Statistical Considerations

Statistical analysis will be described in a separate Statistical Analysis Plan.

Briefly, with respect to sample size: the primary endpoint will be the proportion of responders, i.e., patients who are MRD-negative with sCR at the Day 28 Visit. This is an open-label study, and the null hypothesis is that the responder rate will not differ from the natural rate of MRD-negative sCR at the end of consolidation, as observed in the literature. We determined that this natural rate is 10%.^{19,31,64,69-73} For purposes of power calculations, we assume that the response rate will be 35%. With these assumptions, a sample size of 34 will provide 80% power to detect a one-tailed difference at the 95% confidence level.

7 Ethical Considerations

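### Some Grade 4 organ events that count towards the study pause fall outside the 24-hour notice and need only reach the eCRF within 10 working days

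*Combined protocol and SAP*

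**What the plan says.** Section 5.5 gives two safety reasons to pause. One is fatal: "There is death that is reasonably attributed to study drug within the first 30 days after first infusion". The other is "Two subjects with Grade 4 adverse events to vital organs that are assessed as probably or definitely related to study drug", within 14 days after the last infusion. Once the study is paused, the investigator and study team "will meet in person or by teleconference within 24 hours of the event". Under section 5.3 the medical monitor brings together safety information from the sites and applies the stopping criteria.

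Reporting runs on two tracks:

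- **Expedited.** Under 5.2.5 an SAE or SUSAR "must be reported to the Sponsor within 24 hours of learning of its occurrence". Section 5.2.5.1 repeats this, and its scope is "Any SUSAR and SAE as defined in" section 5.1.
- **Routine.** Under 5.2.4, "Adverse events should be entered into the eCRF system within 10 working days from the knowledge of the event took place". The same section also says that information on adverse events should be "recorded immediately in the source document, and in the appropriate adverse event module of the case report form". Neither sentence requires notice to the Sponsor or the medical monitor.

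Section 5.1.4 makes Grade 4 serious by rule only for CRS, infusion reaction and neurotoxicity. Other Grade 4 events become SAEs through hospitalisation (other than the fever observation of about 24 hours), incapacity, or an important-medical-event judgment, which is optional.

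**The concern.** The pause trigger is defined by grade, organ and relatedness. The expedited track is defined by seriousness or unexpectedness. The two definitions overlap without coinciding, so an event can count towards the pause while no prompt notice is owed to the person who applies it.

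This matters most when the two subjects are at different sites, because neither site can tell that its event is the second in the trial. Until the medical monitor holds both reports, infusions continue in other patients.

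**Working it through.** **1. The plan's own figure.** Section 3.2.1 gives 25 x 10^6 cells/kg on Days 1, 4, 8, 11, 15 and 18. Six doses make 6 x 25 = 150 x 10^6 cells/kg, as stated. The course spans 18 - 1 = 17 days.

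**2. Which pause-qualifying events are expedited.**

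| Event | 24-hour notice? |
|---|---|
| Death attributed to study drug within 30 days of first infusion | Yes, SAE under 5.1.4 |
| Grade 4 CRS, infusion reaction, neurotoxicity | Yes, SAE by rule |
| Grade 4 organ event with hospitalisation | Yes, except the mandated fever observation |
| Related Grade 4 organ event, not admitted | Only through incapacity, an optional judgment, or a literal reading of the SUSAR definition |

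The SAE reporting period ends 30 days after the last infusion (5.2.1), so it covers the 14-day pause window. The gap lies in the type of event, not in the period.

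**3. Is the last row empty?** Section 4.5.1 names Grade 4 transaminase, bilirubin, BUN and creatinine elevations, and exempts those lasting under 7 days from removal from treatment. Removal therefore gives no alert for these. Under 5.1.1 such a value is an AE if, for example, it needs intervention or is judged of significant clinical impact; admission is not required. Patients may be discharged after two hours (3.3.3), and chemistry is drawn on Days 1, 8 and 15 (4.1.2). The row is not empty.

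**4. Ten working days in calendar days,** ignoring holidays: 14 if the event becomes known on Monday to Friday, 13 on Saturday, 12 on Sunday.

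**5. Infusions in another patient, worst case.** Let Day 1 fall on the day the second event becomes known.

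- 12 or 13 days: the deadline is Day 13 or 14. Infusions on Days 1, 4, 8 and 11 have been given: 4 of 6, or 100 x 10^6 cells/kg.
- 14 days: the deadline is Day 15. The count is 4 before that day, or 5 of 6 (125 x 10^6 cells/kg) if the Day 15 infusion precedes entry.

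**6. Randomly timed patient.** Let the day of knowledge fall on study day s, uniform over 1 to 18, and count infusions on days x with s < x <= s + L. Each infusion day x is counted for min(x - 1, L) values of s, so the mean is the sum of min(x - 1, L) over the six days, divided by 18.

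- L = 12: (0 + 3 + 7 + 10 + 12 + 12)/18 = 44/18 = 2.44
- L = 13: (0 + 3 + 7 + 10 + 13 + 13)/18 = 46/18 = 2.56
- L = 14: (0 + 3 + 7 + 10 + 14 + 14)/18 = 48/18 = 2.67

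**7. With a 24-hour notice.** One day to notify and one to meet gives L = 2. Infusions are at least 3 days apart, so at most 1 falls in the gap. The mean is (0 + 2 + 2 + 2 + 2 + 2)/18 = 10/18 = 0.56.

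**8. The two 24-hour clocks.** The meeting is timed from the event, and SAE reporting from learning of it. If a site learns of an SAE a day after onset and reports a day later, the report is on time but the meeting deadline has passed. On the routine track the entry limit falls 12 - 1 = 11 to 14 - 1 = 13 days after the meeting deadline, even if the event is known at once.

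**The case against.** The best reply is that most of the safety net works. The CAR T-cell toxicities that section 3.3.4 names as significant, CRS and neurotoxicity, are expedited at Grade 4, and so are deaths and nearly all hospitalised events. A Grade 4 organ value that meets 5.1.1 and is judged related is a strong candidate for an important medical event. Section 5.1.3 defines unexpectedness without restating seriousness, so read literally it could expedite an unlisted Grade 4 event. Section 5.2.4 also says to record immediately, and the medical monitor consults with sites.

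This narrows the gap and does not close it. The important-medical-event route is optional. The SUSAR heading itself says serious, and what counts as unlisted depends on an investigator brochure that is not in the documents. Immediate recording conflicts with the 10-working-day limit in the same section and requires no notice to anyone. By contrast, section 5.4 requires a deviation that compromises safety to reach the medical monitor within three business days.

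Three stronger readings are tempting and should be resisted:

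- A reader might infer that the pause rule has no data feed, or cannot work. The first three rows of the table show otherwise.
- A reader might infer that the pause waits for the meeting. In 5.5 the meeting follows the pause.
- A reader might take 5 of 6 infusions as the expected exposure. It requires last-day entry, a patient starting on the day of knowledge, a Day 15 infusion given before entry, and no other communication. A 24-hour notice would not reliably prevent the infusion on the day of knowledge either, so the excess over a prompt notice is 5 - 1 = 4 infusions at the extreme, and 4 - 1 = 3 otherwise.

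**Conclusion.** The gap is real but limited. It concerns related Grade 4 vital-organ events that are neither SAEs nor clearly SUSARs, chiefly laboratory elevations without admission. For these, following the plan as written can delay a safety pause that the plan itself sets.

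The counts in the working rest on entry at the deadline, no earlier word to the medical monitor, and an overlapping patient. The visible text gives no stagger, accrual rate or number of sites, so overlap is assumed. A single site that saw both events would know of them at once. The mismatch between the meeting clock and the reporting clock is a separate drafting fault and affects SAEs as well.

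Both are worth correcting, because they bear on a stated safety rule and cost little to repair.

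**What to change.** - **5.2.5.1:** add that any adverse event of Grade 4 or higher affecting a vital organ, judged probably or definitely related to Descartes-11 and falling within the 5.5 pause window, is notified to the Sponsor and the medical monitor within 24 hours of knowledge, whether or not it meets the SAE definition.
- **5.5:** start the meeting clock at notification of the triggering event, in place of "within 24 hours of the event to have a thorough discussion of the event".
- **5.2.4:** reconcile immediate recording with the 10-working-day limit.

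The cost is a few sentences and a small number of extra expedited notices. The pause threshold, dosing and clinical management stay as they are.

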1.1 Study Objectives

1.1.1 Primary Objective

To assess Minimal Residual Disease (MRD)-negative Complete Response (sCR) rate after consolidation treatment with Descartes-11 in patients with high-risk myeloma who have residual disease following induction therapy.

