2.2.4 Early Withdrawal of Subjects

Patients who do not complete at least one Descartes-11 infusion will be considered to have prematurely discontinued the study. The reasons for premature discontinuation must be recorded on the case report form. Final study evaluations will be completed at the time of discontinuation. Provided that all protocol requirements are satisfied for the trial to continue safely, patients who withdraw early from the study will not be counted toward study recruitment limits.

[figure not shown]

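### Section 6: 34 patients do not give 80% power for 10% against 35%; a one-sample exact test has 97.8%, and 80% needs 18 to 22 patients

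*Combined protocol and SAP*

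**What the plan says.** Section 6 (Statistical Considerations) defers the analysis: "Statistical analysis will be described in a separate Statistical Analysis Plan". It then gives a short sample-size argument. The primary endpoint is the proportion of patients who are MRD-negative with sCR at Day 28. The comparison is with an external rate: "the null hypothesis is that the responder rate will not differ from the natural rate of MRD-negative sCR at the end of consolidation". That rate is set at 10% from the literature, and 35% is assumed for the power calculation. The conclusion is that "a sample size of 34 will provide 80% power to detect a one-tailed difference at the 95% confidence level".

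Section 6 names no test, formula, responder cut-off, analysis population, interim look or allowance for non-evaluable patients. Sections 1.1.1 and 3.2.1 describe one treated group and no concurrent control. On replacement, Section 2.2.4 says of those who do not complete at least one infusion that "patients who withdraw early from the study will not be counted toward study recruitment limits".

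**The concern.** All the inputs of a one-sample binomial design are in one paragraph, so the stated power can be checked directly. A rise from 10% to 35% is large for a single-arm test, and 34 patients look like too many for only 80% power.

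This is the only statistical calculation in the supplied text. If it is wrong, an ethics committee or regulator has an incorrect reason for the number of patients exposed. Section 7.2 itself treats limiting that number as one side of a balance to be struck.

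**Working it through.** **Inputs (all Section 6).** p0 = 0.10, p1 = 0.35, n = 34, one-sided, α = 0.05 (read from the 95% confidence level), stated power 80%.

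**Step 1: try to reproduce the plan's figure.** None of the one-sample calculations in Steps 2 and 3 gives 80% at n = 34. The figure does match a two-arm calculation. With p̄ = (0.10 + 0.35)/2 = 0.225, the pooled two-proportion formula without continuity correction gives, per arm,

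n = [z₀.₉₅·√(2p̄(1−p̄)) + z₀.₈₀·√(p0(1−p0) + p1(1−p1))]² / (p1−p0)²
= [1.645·√0.34875 + 0.842·√0.3175]² / 0.0625 = 33.4, rounded up to 34.

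Power at 34 per arm is 80.6%. That is a trial of 68 patients with its own control arm. Other two-sample variants give 32 (unpooled: 31.4; arcsine: 31.9) or 42 (pooled with continuity correction: 41.05). The match suggests where 34 came from but does not prove it.

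**Step 2: exact one-sample test.** Take the smallest r with P(X ≥ r | 34, 0.10) ≤ 0.05.

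- r = 6: 0.1185, too large.
- r = 7: 0.0481, acceptable.
- Power: P(X ≥ 7 | 34, 0.35) = 0.978.

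At one-sided 2.5% the cut-off is 8 (type I error 0.0169) and power is 94.7%.

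**Step 3: other one-sample tests at n = 34, one-sided 5%.** The standard errors are √(0.10·0.90/34) = 0.05145 under the null and √(0.35·0.65/34) = 0.0818 under the alternative.

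| Test | z for power | Power |
|---|---|---|
| Normal, null and alternative variances | (0.25 − 1.645·0.05145)/0.0818 = 2.02 | 97.8% |
| Same, continuity-corrected (subtract 1/68) | 1.84 | 96.7% |
| Arcsine | 0.6226·√34 − 1.645 = 1.99 | 97.6% |
| Wald, alternative variance only | 0.25/0.0818 − 1.645 = 1.41 | 92.1% |

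**Step 4: n for 80% power, exact test, one-sided 5%.**

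| n | Reject at | Type I error | Power at 35% |
|---|---|---|---|
| 17 | ≥ 5 | 2.2% | 76.5% |
| 18 | ≥ 5 | 2.8% | 81.1% |
| 21 | ≥ 6 | 1.4% | 79.9% |
| 22 | ≥ 6 | 1.8% | 83.7% |
| 34 | ≥ 7 | 4.8% | 97.8% |

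Power first reaches 80% at 18, dips just below at 21, and stays above from 22. The unexplained number is 34 − 22 = 12 (35%) to 34 − 18 = 16 (47%). The approximations need 13 (normal), 16 (arcsine), 17 (continuity-corrected) or 23 (Wald).

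**Step 5: could an unstated allowance explain 34?** Patients without a completed infusion are already outside the count (Section 2.2.4), so the allowance would have to cover loss after dosing.

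- If such patients are excluded: 1 − 22/34 = 35% to 1 − 18/34 = 47%.
- If they count as non-responders: with the ≥ 7/34 rule, power is 80% at a true rate of 25.5%, so the share is 1 − 0.2548/0.35 = 27%.

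Neither figure appears in the protocol.

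**The case against.** Nobody can show that 80% is right on the stated inputs, but four points on the other side deserve weight.

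- **The exact figures depend on the test.** Section 6 names none. The Wald approximation gives 92.1% rather than 97.8%, and across the one-sample methods n for 80% runs from 13 to 23, so 11 to 21 patients are unexplained rather than 12 to 16. This stands as a qualification. All these sizes are well below 34, and no method gives 80%.
- **The power may not be the wrong number.** The mismatch shows only that the five figures are inconsistent. With a 15% null, assumed here only for illustration, the exact test in 34 patients rejects at 10 or more and has 80.4% power. Section 1.2.7 speaks of exceeding 20% MRD negativity before transplant in patients on bortezomib-based regimens; against a 20% null, power would be 55% (reject at 12 or more). Section 6 nevertheless states 10%, and its sentence must be judged on that. What stands is that calling the error conservative depends on the 10%, and that the sponsor should confirm the inputs before restating the power.
- **The SAP may hold the explanation.** Section 6 is expressly brief, and the test, population or a loss allowance may be set out in the SAP. That cannot be excluded, but the protocol sentence derives its 80% from its own listed assumptions, and that derivation fails.
- **The consequence is small.** On the stated inputs the 80% target is exceeded, and no conclusion of the trial is put at risk. This is right, and it limits how much weight the point should carry.

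**Conclusion.** The concern holds. On Section 6's own inputs (one group, fixed null of 10%, alternative of 35%, one-sided 5%, n = 34) the stated 80% power is wrong: it is 97.8% with the exact binomial test and at least 92.1% with every one-sample alternative tried at that level. With the exact test, 80% power needs 18 patients, or 22 if it must hold at every larger n.

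This rests on reading the 95% confidence level as one-sided α = 0.05, on a single-stage test, on all 34 patients being counted, and on the 10% null being as intended. Under those conditions the error runs in the safe direction and leaves the test's type I error and the endpoint untouched. The failure is confined to the reason given for 34. How 34 was obtained cannot be established from the text.

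**What to change.** First confirm that 10%, 35% and one-sided 5% are the intended inputs. If they are, replace the last sentence of Section 6 with wording such as:

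> An exact one-sided 5% binomial test of 10% in 34 treated patients rejects at 7 or more responders (type I error 4.8%) and has 97.8% power at 35%.

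If the SAP specifies another test or population, the sentence should carry the figures for that choice instead.

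Then add one sentence saying why 34 is kept, for example safety experience or precision. At the responder counts nearest 35%, the exact two-sided 95% intervals are:

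- 12/34: 19.7% to 53.5% (33.8 points wide);
- 8/22: 17.2% to 59.3% (42.1 points);
- 6/18: 13.3% to 59.0% (45.7 points).

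The observed rates differ slightly (35.3%, 36.4% and 33.3%), so the widths are only approximately comparable. If an allowance for non-evaluable patients was intended, state its size and how those patients are counted. If 80% power is the real target, the matching exact-test size is 18 to 22.

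The cost is two sentences in Section 6 and a consistency check of the SAP. On the stated inputs, no change to the null, the endpoint or the number of patients is required.
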